5.1.1.1.4 Missing Data

[figure not shown]
General missing data handling conventions are specified for methodologies in Section 5.1.1.1.3 and summarized as follows:

[figure not shown]
Table 5-3 Missing Data Handling by Endpoint Type

[figure not shown]
Parameter type	Timing	Missing Data Handling
Responder	Treatment Period	
 • If missing headache severity, migraine-associated symptoms, use Observed Cases (OC)

A conservative approach will used to resolve the incompatibility between the answers to the headache recurrence questions at the 24- and 48-hour time points for each treated attack by setting the answer to the recurrence question at the 48-hour time point the same as the answer to the recurrence question at the 24-hour time point, when the 24-hour time point recurrence question indicates headache recurrence between 2 and 24 hours but the 48-hour time point recurrence question indicates either no or a less severe headache recurrence between 2 and 48 hours for the same treated attack.

5.1.1.2 Demographics

5.1.1.2.1 Analysis Populations

The distribution of participants within the analysis populations will be summarized as follows:

Table 5-4 Analysis Population Summaries

Population	Description	Timing	Methodology
Screened Population	Distribution overall and within sites in total Distribution by lead-in study treatment and within extension study in total	—	Categorical counts
ITT, mITT, and Safety populations	Distribution overall and within sites in total and by treatment group Distribution by lead-in study treatment and by extension study treatment	—	Categorical counts

5.1.1.2.2 Participant Disposition

Participant disposition encompasses the distribution of participants who enter, complete, and discontinue each specified analysis period, along with eCRF-reported discontinuation reasons from each respective analysis period. Participant disposition will also be presented for the relevant subgroups including sex, age group, race, CV risk category, and renal function class. The subgroups are defined in the lead-in studies. Participant disposition will be summarized as follows:

Table 5-5 Participant Disposition Summaries

Parameter	Description	Timing	Methodology
Screening disposition ¹	Distribution in the Screened Population in total	Screening Period	Categorical descriptives
Treatment disposition ¹	Distribution in the Safety Population and ITT Population in total and by treatment group for all participants and by subgroups: 
 • by sex, • by age group (<40 years vs ≥40 years) • by age subgroup (<65 years vs ≥65 years) • by race (white vs non-white) • by cardiovascular risk category (high risk, moderate risk, and low risk) • by renal function class (normal, 	Treatment Period	Categorical descriptives

Parameter	Description	Timing	Methodology
	mild renal impairment, moderate renal impairment)		
4 Week Safety Follow-up disposition ¹	Distribution in the Safety Population and ITT Population in total and by treatment group for all participants and by subgroups: 
 • by sex, • by age group (<40 years vs ≥40 years) • by age subgroup (<65 years vs ≥65 years) • by race (white vs non-white) • by cardiovascular risk category (high risk, moderate risk, and low risk) • by renal function class (normal, mild renal impairment, moderate renal impairment) 	Post-treatment Period	Categorical descriptives

¹ Participant disposition will be listed and participants who prematurely discontinued will be listed.

CV risk subgroup will be derived as a categorical variable with three categories based on NCEP ATP III: Category 1 (High Risk): > 20% 10-year CV risk, Category 2 (Moderate Risk): 10 - 20% 10-year CV risk, and Category 3 (Low Risk): <10% 10-year CV risk.

Renal function class will be derived as a categorical variable based on baseline eGFR as shown in Table 5-6. Since only a few participants are classified into the categories of severe renal impairment or ESRD, renal function class for subgroup analyses will focus on the following categories: Normal, Mild renal impairment, Moderate renal impairment. A listing of all AEs for participants with severe renal impairment or ESRD will be provided including treatment group, participant ID, study center, and baseline eGFR.

Table 5-6 Classification of Renal Function Based on Estimated GFR (eGFR)

Stage	Renal Function Class	eGFR ^a (mL/min/1.73m ²)
1	Normal	≥ 90
2	Mild renal impairment	60-89
3	Moderate renal impairment	30-59
4	Severe renal impairment	15-29
5	End Stage Renal Disease (ESRD)	<15 not on dialysis

^a eGFR: estimate of GFR based on a Modification of Diet in Renal Disease (MDRD) equation.

5.1.1.2.3 Protocol Deviations

Protocol deviations will be defined in Protocol Deviation Requirement Specification, including importance classification. Protocol deviations will be summarized as follows:

Table 5-7 Protocol Deviation Summary

Parameter	Description	Timing	Methodology
Major protocol deviations ¹	Distribution in the ITT Population in total and by treatment group	—	Categorical descriptives

¹Protocol deviations will be listed.

5.1.1.2.4 Demographics

Demographics will be summarized in total and by treatment group for the ITT, Safety, and mITT populations, as follows:

Table 5-8 Demographic Summaries

Parameter	Description	Timing	Methodology
Age ¹	Age (years) relative to informed consent date	Informed consent in the lead-in study	Continuous descriptives
Age group	Age group 1: 
 • <20 • 20 to 29 • 30 to 39 • 40 to 49 • 50 to 59 • 60 to 69 • ≥ 70 Age group 2: 
 • <40 • ≥40 Age group 3: 
 • <65 • ≥65 	Informed consent in the lead-in study	Categorical descriptives
Sex, race, and ethnicity ¹	
 • eCRF categories • Race group 
 ○ White ○ Non-white 	Screening Period in the lead-in study	Categorical descriptives

¹Participant demographics will be listed.

5.1.1.2.5 Baseline Characteristics

Baseline characteristics will be summarized in total and by treatment group for the ITT, Safety, and mITT populations as follows:

Table 5-9 Baseline Characteristics Summaries

Parameter	Description	Timing	Methodology
Baseline characteristics ¹	
 • Height (m) • Weight (kg) • Body mass index (BMI) 
 ○ Weight (kg) / height (m)² 	Latest assessment in Screening Period in the lead-in study	Continuous descriptives
Cardiovascular risk ²	Cardiovascular risk factor subgroup 
 • low risk • moderate risk • high risk 	Randomization date in the lead-in study	Categorical descriptives

Parameter	Description	Timing	Methodology
Renal function class ²	Renal function class subgroup 
 • Normal • Mild renal impairment • Moderate renal impairment 	Randomization date in the lead-in study	Categorical descriptives
Randomization strata ³	Previous response to triptans 
 • Triptan Responder • Triptan Insufficient Responder • Triptan Naïve Triptan Insufficient Responder will be further classified into subcategories 
 • Insufficient Efficacy • Insufficient Tolerability • Contraindications/Warnings or Precautions Current use of prophylactic concomitant medication for migraine (Yes, No)	Randomization date in the lead-in study	Categorical descriptives

¹ Participant baseline characteristics will be listed.

² Summary for Safety population only.

³ Participant randomization scheme and codes will be listed.

5.1.1.2.6 Medical History

Medical history, encompassing abnormalities and surgeries reported as occurring before the Screening Visit in the lead-in study, will be coded using the Medical Dictionary for Regulatory Activities (MedDRA), version 20.1 or newer. Unique participants who report medical history events will be summarized by MedDRA system organ class (SOC) and preferred term (PT) in total and by treatment group for the Safety Population as follows:

Table 5-10 Medical History Summary

Parameter	Description	Timing	Methodology
Medical history ¹	Abnormalities and surgeries occurring before the Screening Visit by treatment group	Screening Period in the lead-in study	Categorical descriptives

SOCs will be sorted alphabetically; PTs will be sorted in descending frequency in the highest dose group.

¹ Participant medical history will be listed.

5.1.1.2.7 Migraine History

Migraine history (based on the lead-in study), including diagnosis, duration of disorder, previous use of prophylaxis treatment, average frequency of moderate to severe migraines per month in past 3 months, and acute treatments will be reported in total and by treatment group for the Safety Population as follows:

Table 5-11 Migraine History Summary

Parameter	Description	Timing	Methodology
Migraine Diagnosis ¹	
 • With Aura • Without Aura • Both 	Screening Period in the lead-in study	Categorical descriptives
Previous Prophylaxis Migraine Treatment ¹	Yes or No	Screening Period in the lead-in study	Categorical descriptives
Acute Migraine Treatment ¹	Categorize as Yes or No, and subcategorize the Yes by:	Screening Period in the lead-in	Categorical descriptives

Parameter	Description	Timing	Methodology
	
 • Triptan • Ergot or Ergot Combinations • NSAID • Opiate or Opiate Combination • Antiemetic Agent • Barbiturates • Other 	study	
Migraine Disorder Duration ¹	In the Table summarize in Years, in the Listing show original data in Years and Months	Screening Period in the lead-in study	Continuous descriptives
Average Frequency of Moderate to Severe Migraines per Month in Last 3 Months	N/A	Screening Period in the lead-in study	Continuous descriptives

¹ Participant migraine history will be listed.

5.1.1.2.8 Prior and Concomitant Medications

Medications will be coded using the World Health Organization (WHO) Drug Dictionary, version March 2016 or newer. Unique participants who reported medications will be summarized by Anatomical Therapeutic Chemical (ATC) 4 class and PT in total and by treatment group for the Safety Population as follows:

[figure not shown]
Table 5-12 Medication Summaries

[figure not shown]
Parameter	Description	Timing	Methodology
Prior medications ¹	Medications taken \geq 1 time before the study treatment start date of the lead-in study, regardless of medication end date	Screening Period in the lead-in study	Categorical descriptives
Concomitant medications ¹	Medications taken \geq 1 time on or after the randomization date, regardless of medication start date	Treatment Period	Categorical descriptives

[figure not shown]
ATC4 classes will be sorted alphabetically; PTs will be sorted in descending frequency in the highest dose group.

¹ Participant prior and concomitant medication will be listed.

[Redacted content]

5.1.1.4 Safety Analyses

Safety analyses will be based on the Safety Population.

Baseline assessments for applicable safety endpoints are defined as follows:

Table 5-16 Safety Endpoint Baseline Definitions

Parameter	Description	Timing

• Clinical laboratory evaluations• Vital signs• Electrocardiograms (ECGs)	eCRF- or (standardized) vendor-provided assessments	Latest non-missing assessment before the first dose of treatment in the lead-in study

5.1.1.4.1 Study Treatment Exposure and Compliance

Study treatment exposure will be listed for the Safety Population.

The listing of treatment exposure will indicate whether the participant took the optional second dose in addition to the first dose for each attack.

For safety analyses only, the number of treated migraine attacks will be determined based on the date and time (if available from eDiary) doses were taken. Starting with the first dose taken by each participant, doses will be sorted based on the date and time (if available from eDiary) each dose was taken. Subsequent doses that are separated by at least 2 calendar days or 48 hours will be considered the initial treatment for a separate and distinct migraine attack. Doses taken within the 2-calendar day/48-hour window of the initial dose will be considered as additional doses treating the same attack. As such, the treatment label (initial dose or optional second dose) will be ignored. The extent of exposure to study treatment will be summarized as follows:

Table 5-17 Treatment Exposure Summaries

Parameter	Description	Timing	Methodology
Number of participants with study participation by 3-month interval	
For all participants:
 
 total number (%) of participants who completed 3 months total number (%) of participants who completed 6 months total number (%) of participants who completed 9 months total number (%) of participants who completed 12 months 
Subgroup analyses:
 
 by Sex by Age Group: <40 vs ≥40 by Age Group: <65 vs ≥65 by Race White vs All other races by CV risk category by renal function class 	Treatment period	Categorical descriptives
Number of participants with study participation by 3-month interval among those who treated at least 2 migraine attacks per month on average during the completed interval	
 total number (%) of participants who completed 3 months total number (%) of participants who completed 6 months total number (%) of participants who completed 9 months total number (%) of participants who completed 12 months 	Treatment period	Categorical descriptives
Number of migraine attacks treated over the entire duration of the study ¹	
 total number of migraine attacks treated with only one dose total number of migraine attacks treated with two or more doses total number of doses taken 	Treatment period	Continuous descriptives
Number of attacks treated with study treatment per month ¹	
 ≥ 8 ≥ 6 and < 8 ≥ 4 and < 6 ≥ 2 and < 4 < 2 	Treatment period	Categorical descriptives
Average number of attacks treated with study treatment per month ¹	
For all participants:
 
 ≥ 8 ≥ 6 and < 8 ≥ 4 and < 6 ≥ 2 and < 4 < 2 
Subgroup analyses:
 
 by Sex by Age Group: <40 vs ≥40 by Age Group: <65 vs ≥65 by Race White vs All other races by CV risk category by renal function class 	Treatment period	Categorical descriptives
Maximum number of attacks treated with study treatment per	
 ≥ 8 ≥ 6 and < 8 ≥ 4 and < 6 	Treatment period	Categorical descriptives

Parameter	Description	Timing	Methodology
month, defined as maximum of monthly total number attacks treated with study treatment among months 1-12 for each participant ¹	
 • ≥ 2 and < 4 • < 2 		
Number of months with the number of attacks treated with study treatment in each category ¹	For each category: 
 • ≥ 8 • ≥ 6 and < 8 • ≥ 4 and < 6 • ≥ 2 and < 4 • < 2 	Treatment period	Categorical descriptives
Average number of study treatment taken per month ¹	
 • ≥ 16 • ≥ 14 and < 16 • ≥ 12 and < 14 • ≥ 10 and < 12 • ≥ 8 and < 10 • ≥ 6 and < 8 • ≥ 4 and < 6 • ≥ 2 and < 4 • < 2 	Treatment period	Categorical descriptives

Analysis visits defined in Section 6.2.2.

¹ Participants in the ubrogapant treatment arms only. No imputation for the last incomplete month.

Treatment compliance for this study will be summarized as follows:

Table 5-18 Treatment Compliance Summaries

Parameter	Description	Timing	Methodology
Overdosing ¹	Participants who took more than 2 doses within 48 hours or 2 calendar days (if time information is not available)		Listing

¹ Participants in the ubrogapant treatment arms only.

5.1.1.4.2 Adverse Events

The following adverse event (AE) terms are defined:

Table 5-19 AE Terms

Term	Description
Treatment-emergent	An event that initially occurs or increases in intensity on or after the initial dose of treatment of the lead-in study. An event that occurs after Visit 16 for participants with Visit 16, or more than 30 days after the last visit or last treatment, whichever is later, for participants without Visit 16 will not be considered as treatment-emergent.

Term	Description
On-therapy	An event where: 
 • Treatment start date of the lead-in study \leq event start date \leq Visit 16 for participants with Visit 16, or within 30 days after the last visit or last treatment, whichever is later, for participants without Visit 16

AEs, encompassing abnormalities and surgeries reported as occurring after the Screening Visit, will be coded using MedDRA version 20.1 or newer. Unique participants reporting AEs in the following AE categories will be summarized by treatment group for the Safety Population as follows:

Table 5-20 AE Summaries

Parameter	Description	Timing	Methodology
Overall summary	Overall summary only for the following categories: 
 • Treatment-emergent AEs (TEAEs) • Treatment-related TEAEs • On-therapy serious adverse events (SAEs) • Deaths • AEs leading to discontinuation Subgroup analyses by Cardiovascular Risk Category and by renal function class	From randomization date to Visit 16 for participants with Visit 16, or within 30 days after last visit or last treatment, whichever is later, for participants without Visit 16	Categorical descriptives
TEAEs	Summary by 
 • SOC and PT for all participants and by subgroup analyses: 
 ○ by Sex ○ by Age Group <40 vs \geq40 ○ by Age Group <65 vs \geq65 ○ by Race White vs All other races ○ by cardiovascular risk category ○ by renal function class • SOC and PT for concomitant medication classes used by at least 10% of participants in at least one treatment group • SOC, PT, and AE onset time intervals 
 ○ <3 months ○ \geq3 and <6 months ○ \geq6 and <9 months ○ \geq9 and <12 months ○ \geq12 months • SOC, PT, and average number of migraine attacks treated with study treatment per month 
 ○ \geq2 ○ \geq4 ○ \geq6 	From randomization date to Visit 16 for participants with Visit 16, or within 30 days after last visit or last treatment, whichever is later, for participants without Visit 16	Categorical descriptives

Parameter	Description	Timing	Methodology
	
 ○ ≥8 • SOC, PT, and severity • SOC, PT, and causal relationship to the study treatment • Type (Mild, Moderate, Severe, related, not related) • SOC and PT for TEAEs occurring in ≥ 2% of participants in any ubrogapant treated dose group (and greater than placebo) 		
Common TEAEs	Summary by PT 
 • Includes TEAEs occurring in ≥ 2% of participants in any treatment group 	From randomization date to Visit 16 for participants with Visit 16, or within 30 days after last visit or last treatment, whichever is later, for participants without Visit 16	Categorical descriptives
On-therapy SAEs ¹	Overall summary and by PT	From randomization date to Visit 16 for participants with Visit 16, or within 30 days after last visit or last treatment, whichever is later, for participants without Visit 16	Categorical descriptives
On-therapy fatal SAEs	Participants who report On-therapy fatal SAEs will have their fatal SAEs and all AEs listed	From randomization date to Visit 16 for participants with Visit 16, or within 30 days after last visit or last treatment, whichever is later, for participants without Visit 16	Categorical descriptives
AEs leading to discontinuation ²	Overall summary and by PT	From randomization date to Visit 16 for participants with Visit 16, or within 30 days after last visit or last treatment, whichever is later, for participants without Visit 16 ²	Categorical descriptives
TEAEs of specific interest ³	Overall summary and by PT for the following type of TEAEs: 
 • Hepatic Injury TEAEs • Cardiac Arrhythmias TEAEs • Central Nervous System Vascular Disorders TEAEs • Embolic and Thrombotic Events TEAEs • Hypertension TEAEs • Ischaemic Heart Disease TEAEs • Suicide/self-injury TEAEs • Triptan-associated TEAEs • Abuse-related TEAEs 	From randomization date to Visit 16 for participants with Visit 16, or within 30 days after last visit or last treatment, whichever is later, for participants without Visit 16	Categorical descriptives

SOCs will be sorted alphabetically; PTs will be sorted in descending frequency in the highest dose group.

If more than 1 AE is coded to the same participant, the participant will be counted only once for that preferred term using the greatest severity

Parameter	Description	Timing	Methodology
-----------	-------------	--------	-------------

If more than 1 AE is coded to the same participant, the participant will be counted only once for that preferred term using the strictest causal relationship to treatment for the summarization by causal relationship

¹ Participants who report ≥ 1 SAE will have their SAE listed.

² If the discontinued date is from randomization date to Visit 16 for participants with Visit 16, or within 30 days after last visit or last treatment, whichever is later, for participants without Visit 16, then AEs leading to discontinuation will be summarized and listed

³ Participants who reported ≥ 1 AEs in the corresponding category will have these AEs listed.

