4.1 Study Design Summary

Structure: Multicenter, randomized, open-label, 52-week extension study; randomization to the ubrogepant arms (50 and 100 mg) will be blinded.

Duration: 52 weeks

Study Treatment Groups: usual care, ubrogepant 50 mg, or ubrogepant 100 mg

Controls: Not applicable

Dosage/Dose Regimen: Patients randomized to either of the ubrogepant arms will treat up to 8 migraine attacks (of any pain severity) every 4 weeks at home for a total 1 year. Patients have the option to take a second dose of ubrogepant if the patient has either a nonresponding migraine or a migraine recurrence. The second dose of ubrogepant will be identical to the first dose.

Patients randomized to the usual-care arm will be instructed to treat their migraine with medications that they routinely use to relieve a migraine attack.

Randomization: [REDACTED] Patients will be randomized (1:1:1) to 1 of the following 3 treatment groups: usual care, ubrogepant 50 mg, or ubrogepant 100 mg. The study is open-label; however, randomization to the ubrogepant arms (50 and 100 mg) will be blinded.

[REDACTED]

Number of Participants: Approximately 1200 patients will be randomized (400 patients per arm) from approximately 200 centers in the United States.

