5.1.1.1.3 Statistical Methodology

The methodologies defined below apply as specified to individual endpoints defined in this SAP. All statistical tests will be 2-sided hypothesis tests performed at the 5% level of significance for main effects. All confidence intervals will be 2-sided 95% confidence intervals, unless stated otherwise.

Table 5-2 Statistical Methodology

Methodology	Description
M1 Categorical counts	
 • Number of participants in individual categories 
 ○ Participants with ≥ 1 qualifying event counted once per individual category
M2 Categorical descriptives	
 • Number and percentage of participants in individual categories 
 ○ Participants with ≥ 1 qualifying event counted once per individual category • N1 if proportion denominator \neq number of participants in the population (standard percentage denominator) 
 ○ N1 = participants with non-missing baseline value
M3 PCS descriptives	
 • Number and percentage of participants meeting potentially clinically significant (PCS) criteria 
 ○ Participants with ≥ 1 qualifying event counted once per PCS category • Percentage denominator = number of participants with all non-missing non-PCS baseline and ≥ 1 non-missing postbaseline assessment 
 ○ Unevaluable assessments considered missing
M4 Shift analysis	
 • Number and percentage of participants in individual baseline and postbaseline categories • Percentage denominator = number of participants in individual baseline categories • N1 = participants with non-missing values at both baseline and the specified postbaseline analysis visit
M5 Continuous descriptives	
 • N1, mean, standard deviation (SD), median, minimum, maximum • N1 = participants with non-missing value
M6 CFB descriptives	
 • Continuous descriptives for baseline, postbaseline, and change from baseline (CFB) values • N1 = participants with non-missing values at both baseline and the specified postbaseline analysis visit

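### The SAP's table of TEAEs by concomitant-medication class has no readable timing rule, so drugs started to treat an event can create class-event associations and distort arm comparisons within a class

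*SAP*

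**What the plan says.** The TEAE row of SAP Table 5-20 (section 5.1.1.4.2) includes a breakdown by "SOC and PT for concomitant medication classes used by at least 10% of participants in at least one treatment group". It does not say how the drug must be timed relative to event onset. Its event window runs "From randomization date to Visit 16 for participants with Visit 16", with a 30-day rule for the others. Its method is categorical descriptives, for which SAP 5.1.1.1.3 has each participant's "qualifying event counted once per individual category".

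SAP 5.1.1.2.8 (Table 5-12) holds the only readable definition of a concomitant medication: one taken at least one "time on or after the randomization date, regardless of medication start date". The class level is given there too: "Unique participants who reported medications will be summarized by Anatomical Therapeutic Chemical (ATC) 4 class and PT".

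Protocol 4.5.1 bars triptans, ergots, opioids, NSAIDs, other analgesics, antiemetics and proton pump inhibitors in the 48 hours before ubrogepant, and exempts the usual-care arm. Protocol 5.6.2 has usual-care patients treat attacks with their routine drugs, with no cap on the number of attacks.

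**The concern.** Class membership is decided after randomization, and the event being tabulated can itself decide it. A patient who has nausea and then takes an antiemetic joins the antiemetic class, and that nausea is counted there. The other breakdowns by patient subgroup do not have this problem: SAP 5.1.1.2.2 says that the sex, age, race, cardiovascular-risk and renal subgroups are defined in the lead-in studies.

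Two things are at stake. First, a class row may show a high event rate that reflects treatment of the event rather than any effect of combining drugs. Second, usual care is there to put the ubrogepant safety findings in context. If class use for other reasons differs between arms, as the protocol's restrictions make plausible, the event-driven users weigh differently in each arm. The table is also due at the interim, which covers all SAP analyses except efficacy (SAP 5.1.1.6).

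**Working it through.** The plan gives no figure for this table, so there is none to reproduce. The design figure is 400 patients per arm (SAP 4.1), so the 10% rule needs 0.10 × 400 = 40 users in an arm.

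**Assumed inputs (not in the documents).** b is the share using the class for reasons unrelated to the event. r is the event risk, the same for everyone, so the class has no effect. t is the share of events, in patients not already using the class, that are treated with it.

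**Formulas under the Table 5-12 definition.**
- Users = b + (1 − b)rt
- Event risk in users = [br + (1 − b)rt] / users
- Event risk in non-users = r(1 − t) / (1 − rt)

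**Two arms with r = 5% and t = 25% in both, differing only in b:**

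| Per 400 patients | b = 10% | b = 40% |
|---|---|---|
| Users for other reasons, 400b | 40 | 160 |
| Events among them, 400br | 2 | 8 |
| Users added by treating the event, 400(1 − b)rt | 4.5 | 3 |
| Users as counted | 44.5 | 163 |
| Event rate, users | 6.5/44.5 = 14.6% | 11/163 = 6.7% |
| Event rate, non-users | 13.5/355.5 = 3.8% | 9/237 = 3.8% |

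Every added user has the event. Among users the arm ratio is 14.6/6.7 = 2.2, although the true ratio is 1. Within an arm, the ratio of users to non-users is 3.85 at b = 10% and 1.78 at b = 40%.

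**Range.**
- With r from 2% to 10%, t from 10% to 50%, and background pairs of 10/40, 20/40 and 10/20%, the false arm ratio among users runs from 1.2 to 2.9.
- If b, r and t are all equal across arms, the arm ratio is 1.00. If t = 0 (the class is not used for that event), the ratio of users to non-users is also 1.00.
- With b = 10% and t = 50% in both arms and true risks of 5% v 10%, the arm difference is 15.5 points in users and 2.7 in non-users. The true difference is 5.0 points in both.
- Treatment use can lift a class over the threshold: b = 8%, r = 5%, t = 50% gives 0.08 + 0.92 × 0.025 = 10.3% users.

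**After the fix.** If membership is fixed by use at randomization, the added users disappear. The rates return to 2/40 = 5.0% and 8/160 = 5.0%, and non-users are also at 5.0%.

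**The case against.** A reader might infer that this is the trial's drug-interaction analysis and that it will report false interactions. The documents do not support that. The SAP does not give the row that purpose. It plans no test or model on it and specifies no column for non-users, and adverse events are summarized by treatment group. The ratios of users to non-users above therefore describe how a row could be misread, not a planned comparison.

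Other points also stand:
- The SAP does not say that Table 5-12 governs the Table 5-20 row. That is the natural reading, but table specifications are in a separate document and parts of SAP section 6 are blacked out, so a timing rule could exist there.
- The bias shrinks as background use rises, and background use of analgesics and antiemetics may be high in these patients.
- Protocol 9.1.1 keeps symptoms collected as efficacy variables and clearly due to the disease out of AE reporting, which may remove some migraine nausea or pain.
- Concomitant medications will be listed by participant, so the order of drug and event could be checked case by case.

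One defence holds only in part. The planned arm comparison within a class is unbiased under no effect if event risk, treatment of events and background use are all equal across arms. The protocol's different medication rules make the last condition doubtful.

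**Conclusion.** The point holds in limited form. As readable, the table lets an event place a patient in the class under which that event is counted. It can therefore show associations between a class and an event that come from treating the event, and it can distort arm comparisons within a class. By this mechanism the effect is confined to classes used to treat the event concerned.

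Its size rests on assumptions. For the inputs shown, the false arm ratio among users is 2.2, with a range of 1.2 to 2.9 over the grid. If class use is lower on ubrogepant than in usual care, the error runs against ubrogepant. Patients followed for longer may also collect both more drugs and more events; that was not quantified.

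The overall TEAE, SAE and hepatic summaries do not use this classification and are unaffected. This is a cheap improvement to one descriptive safety table, and no primary conclusion depends on it.

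**What to change.** In SAP Table 5-20, define class membership by medication in use at the randomization date and apply the 10% rule to that. Tabulate TEAEs after randomization by arm, separately for users and non-users, with the N of each shown. State how as-needed drugs and partial start dates are classified. Membership then precedes every counted onset and is a baseline factor that randomization should balance. SSRIs, SNRIs and migraine prophylactics are captured, since Protocol 4.5.1 has them continue unchanged from the lead-in study.

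If on-study use is also shown, count only events whose onset falls while the drug, started before onset, was in use. Take exposed participants or exposed person-time as the denominator. Restricting the numerator alone is not enough, so without a matching denominator this version should be omitted.

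The cost is a short addition to the SAP and one derived flag. No new data should be needed, since medication changes are asked about at each visit (Protocol 8.7). The downside is that fewer classes will reach 10%, and drugs first started during the study drop out of the main version.
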